6.3 Exclusion Criteria

PART A / Epidemiologic Investigation:

N/A

PART B / Water Biofilm Collection:

N/A

6.4 Study Specific Tolerance for Inclusion/Exclusion Criteria

N/A

6.5 Screen Fail Criteria

N/A

7 CONCURRENT MEDICATIONS

7.1 Allowed Medications and Treatments

No available therapy for CF is restricted.

7.2 Prohibited Medications and Treatments

N/A

8 STUDY TREATMENTS

Part A (Epidemiologic Investigation) is retrospective collection of epidemiologic data. Part B (Water Biofilm Collection) is exclusively environmental sampling and does not include subject involvement.

9 STUDY PROCEDURES AND GUIDELINES

REDCap data collection is detailed (Appendix 1 and Appendix 2 - Epidemiologic Investigation). Environmental sampling instructions are detailed (Appendix 3).

9.1 Clinical Assessments

9.1.1 Demographics and CFF Registry ID

Demographic information (date of birth, sex, race, zip code) will be recorded. CFF Registry number will be recorded for participating CF participants.

9.1.2 CF Diagnosis

CF diagnosis will be confirmed by the participating Care Center.

9.1.3 NTM History

Results from molecular analysis performed at National Jewish Health Mycobacteriology and Pharmacokinetics Laboratory will be recorded.

9.1.4 NTM Disease Diagnosis Evaluation

Investigators will record if a diagnosis of CF NTM disease is met based on the US CFF and European CF Society consensus recommendations for the management of NTM in individuals with CF.

9.1.5 NTM Treatment

Investigators will record if the subject underwent or is undergoing treatment of CF NTM disease.

9.1.6 Drug Toxicity Monitoring

N/A

9.2 Clinical Laboratory Measurements

N/A

9.3 Research Laboratory Measurements

N/A

10 EVALUATIONS BY VISIT

Not applicable.

11 ADVERSE EXPERIENCE REPORTING AND DOCUMENTATION

Not applicable. Adverse Events and Serious Adverse Experience will not be reported for this retrospective study.

12 DISCONTINUATION AND REPLACEMENT OF PARTICIPANTS

12.1 Early Withdrawal of Participants from the Study

N/A.

12.2 Replacement of Participants

N/A

13 PROTOCOL VIOLATIONS

A protocol violation occurs when the participant, investigator, or the Sponsor fails to adhere to significant protocol requirements affecting the eligibility criteria and primary endpoint criteria.

Failure to comply with Good Clinical Practice (GCP) guidelines may also result in a protocol violation.

There will be no protocol violations. We will monitor for protocol deviations. If deviations are identified, we will request modifications as necessary to meet protocol guidelines.

14 DATA SAFETY MONITORING

N/A

15 STATISTICAL METHODS AND CONSIDERATIONS

15.1 General Considerations

For each of the primary and secondary outcomes, biostatistical analysis of the multicenter data will be completed using both qualitative and quantitative approaches. We will identify a set of variables used to assess degree of proximity of subjects in time and/or space. For example, two subjects with neighboring rooms at a hospital would have close proximity, but proximity would be increased for two subjects at a facility that had longer overlap time, relative to a pair of subjects that had shorter overlap. We will explore creating composite measures of quantitative proximity that incorporate multiple variables. Qualitative measures of proximity, such as location type (testing laboratory, patient room) will also be assessed. Several testing approaches will be used to compare the relationship between similarity of strains and degree of proximity of subjects. In the simplest form, descriptive statistics will be computed for proximity variables, for pairs of subjects who are determined to have similar strains versus those who have dissimilar strains, and multivariate or 2-sample t-tests will be performed to test for differences between these groups. More advanced modeling will be performed to determine the relationship between the degree of similarity in strains with the proximity and subject characteristic variables; multiple linear regression will be used when considering continuous strain similarity, while multiple logistic regression will be used when considering subjects with dichotomized (similar/dissimilar) strains to other subjects.

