1.2 Overview of Preliminary Studies

When the CO-RDP receives NTM clinical isolates from around the U.S., DNA is sequenced via WGS and analyzed for genetic relatedness at the core genome level. Mycobacterial DNA is sequenced using Illumina MiSeq 2X300 chemistry. Sequence reads are mapped to the appropriate mycobacterial reference genome and compared to find phylogenomic differences at the SNP level. As of January 2019, over 1,000 CF NTM isolates from 631 patients at 92 contributing facilities have *been banked*. To date, 904 CF NTM isolates *have been sequenced from 79 U.S. Care Centers, representing a total of 13 predominant NTM species and subspecies (Figure 2)*. To determine a threshold of genetic similarity for highly similar isolates, pairwise SNP distances in the core genome were calculated between all pairs of “same” (within-patient) or “different” (between-patient) isolates. We observed that 25 or fewer SNPs define background similarity of same-patient isolates for MAB and MMAS. Thus, a conservative threshold of 15 SNPs was chosen to define genetic clusters between patients, representing likely transmission events or shared source acquisition.

Findings: Unpublished data from the CO-RDP of 114 isolates from CF MAB patients across the country demonstrates 26 of 114 (23%) had isolates in highly related clusters. *Twelve of 114 (11%) had isolates in clusters and received care in the same Center. Clusters are occurring among multiple *M. abscessus* subspecies as well as *Mycobacterium avium* complex (MAC) subspecies.*

Preliminary results from one Care Center utilizing the HALT NTM toolkit investigated six clusters of patients with highly similar respiratory NTM isolates, including *M. abscessus* and MAC. The size of the highly related clusters ranged from 2-3 patients. Among the six identified NTM clusters, two clusters occurred with MAB, one with MMAS, *two with *M. avium* (MAV), and one with *M. intracellulare**. No patients within a cluster are related or living together. This is the first description of a MAC cluster.

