15.1.1 Data Sets Analyzed

All analyses will be based on the group of subjects that are identified by the CO-RDP as having NTM isolates, defined as highly similar strains at the genomic level, harbored by two or more patients within a single Care Center.

152 Demographic and Baseline Characteristics

The following baseline demographic and clinical characteristics will be reported: age, gender, race, ethnicity, zip code, and NTM sub/species.

153 Analysis of Primary Endpoint

PART A / Epidemiologic Investigation:

The primary endpoint will characterize the origins and prevalence of healthcare-associated patient-to-patient transmission of NTM among different CF Care Centers. We will further characterize the source(s) of direct or indirect transmission of NTM within an individual CF healthcare setting. We will identify a set of variables used to assess degree of proximity of subjects in time and/or space. For example, two subjects with neighboring rooms at a hospital would have close proximity, but proximity would be increased for two subjects at a facility that had longer overlap time, relative to a pair of subjects that had shorter overlap. We will explore creating composite measures of quantitative proximity that incorporate multiple variables. Qualitative measures of proximity, such as location type (testing laboratory, patient room) will also be assessed. Several testing approaches will be used to compare the relationship between similarity of strains and degree of proximity of subjects. In the simplest form, descriptive statistics will be computed for proximity variables, for pairs of subjects who are determined to have similar strains versus those who have dissimilar strains, and multivariate or 2-sample t-tests will be performed to test for differences between these groups. More advanced modeling will be performed to determine the relationship between the degree of similarity in strains with the proximity and subject characteristic variables; multiple linear regression will be used when considering continuous strain similarity, while multiple logistic regression will be used when considering subjects with dichotomized (similar/dissimilar) strains to other subjects.

PART B / Water Biofilm Collection:

The primary endpoint will characterize clinically-relevant NTM found in water biofilms within CF healthcare settings and determine if the biofilm isolates are highly related to isolates recovered from patients.

154 Analysis of Secondary Endpoints

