APPENDIX 2 REDCAP USER GUIDE

So, you've received a letter from National Jewish Health Advanced Diagnostic Laboratories (NJH ADx) saying you have patients at your center with a highly similar strain of NTM. Now what?

1. Contact [name] at NJH. She will help you with initial questions regarding study design and study start-up, including IRB and database requirements.
2. For NJH REDCap access, you will be sent a link to complete REDCap training. You will be asked the following:
 - For the question "Are you an employee of National Jewish Health?" select No.
 - Explain your affiliation as "HALT NTM"
 - National Jewish Health Sponsor is "[name]"
 - For department, indicate your CF center/institution name.
 - Complete the rest as indicated.
 - Email [name] or [name] once you've been given access so you can be added to the project.
3. Now you have access to the database. Log on to REDCap. On the welcome screen, open the HALT NTM project.
4. On the left hand side under Applications, open the File Repository. Download the HALT NTM cheat sheet.
5. Print a HALT NTM cheat sheet for each unique pair:
 - If there are two patients listed on your letter, you will have one unique pair.
 - If there are three patients listed on your letter, you will have three unique pairs.
 - If there are four patients listed on your letter, you will have six unique pairs.
 - This is because the date ranges are compared between two subjects and is unique for each pair.
6. Complete the first six lines on the HALT NTM cheat sheet for each unique pair. You will need to refer to it during pairing and data extraction.
7. Back in REDCap, on the left hand side under Data Collection, click Add / Edit Records. On the Add/Edit Records page, click on the button Add new record. You will be taken to the Record Home Page. There will be a NEW Study ID XXX-XX. Record that number (XXX-XX) on the HALT NTM cheat sheet. It is auto-generated by REDCap. You will need it later.
8. The first Form to complete is Demographics. Open the form by clicking on the circle under Demographics. Near the top of the form under the header **Pairs Survey** is a link to the "**Finding Pairs survey**." Click on the link. You will be taken to an interactive tool that will help you determine if this subject is "subject 1" or "subject 2" in this pairing.

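### Part A tests pairs of patients with a 2-sample t-test as if they were independent, although pairs share patients and Centers, so its error rate is not controlled in either direction

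*Protocol*

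**What the plan says.** Section 15.1 sets out the Part A analysis, and 15.3 (Analysis of Primary Endpoint) and the synopsis repeat it. Proximity variables are summarized "for pairs of subjects who are determined to have similar strains versus those who have dissimilar strains", and then "multivariate or 2-sample t-tests will be performed to test for differences between these groups". The unit is therefore the pair. More advanced modeling follows: "multiple linear regression will be used when considering continuous strain similarity", with logistic regression, worded by subject, for dichotomized similarity. None of these sections names a random effect, a robust variance, stratification by Center or a permutation.

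Appendix 2, step 5 gives the pairing rule: "If there are three patients listed on your letter, you will have three unique pairs"; four patients give six. It adds: "This is because the date ranges are compared between two subjects and is unique for each pair".

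On the comparison group, the synopsis and 4.1 call for two controls per clustered subject, and the discussion in the background section expects control pairs to show the baseline frequency of overlap. Section 15.1.1, however, says: "All analyses will be based on the group of subjects that are identified by the CO-RDP as having NTM isolates", and limits these to strains shared by two or more patients within one Center.

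**The concern.** A 2-sample t-test takes its standard error from the number of pairs, as if each were a separate observation. Two pairs with a patient in common both carry that patient's attendance pattern, and two pairs from one Center both carry its layout and scheduling. The two kinds of sharing can act in opposite directions. A shared patient makes a group mean more variable than the test assumes. A Center effect present in both groups largely cancels from the difference but still inflates the pooled standard deviation.

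The test stands in the primary endpoint section. If its error rate is unknown, an association between proximity and strain similarity may be declared too often, or a real one missed. Either matters in a study meant to judge healthcare-associated transmission.

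**Working it through.** The protocol states no significance level, variance or calculated sample size, so it has no figure of this kind to reproduce. Its pair counts do reproduce: k(k-1)/2 gives 1, 3 and 6 for k = 2, 3 and 4.

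**Inputs from the protocol.** Up to 20 Centers (15.6); two controls per case (synopsis, 4.1); all pairs within a cluster (Appendix 2). On cluster size, Section 1.2 says: "The size of the highly related clusters ranged from 2-3 patients". Several clusters can occur in one Center: "Preliminary results from one Care Center utilizing the HALT NTM toolkit investigated six clusters of patients".

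**Why the standard error is wrong.** Write a pair's proximity as patient i + patient j + residual, with total variance 1 and patient share vp each. Two pairs sharing one patient then have correlation vp. For the three pairs of a 3-patient cluster, the variance of the mean is (1 + 2vp)/3. With vp = 0.2 (assumed) this is 1.4/3 = 0.467, where the t-test assumes 1/3 = 0.333.

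**Simulation with no true difference.** All of the following is assumed: 15 Centers, one cluster each with sizes alternating 2 and 3, same-Center controls, all within-Center pairs, one common window, two-sided 5% level. Overlaps per pair are Poisson with mean 2 × Center effect × attendance i × attendance j, the effects being log-normal with mean 1.

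Eight clusters of 2 and seven of 3 give:
- cases: 16 + 21 = 37; controls: 74; patients: 111
- similar pairs: 8×1 + 7×3 = 29
- cluster-control pairs: 8×(2×4) + 7×(3×6) = 64 + 126 = 190
- control-control pairs: 8×6 + 7×15 = 48 + 105 = 153

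Actual error of the pooled t-test, in %, by comparator (20,000 studies per row; Monte Carlo SE near 5% is √(0.05×0.95/20,000) = 0.15 points):

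| Attendance CV, Center CV | Control-control | All dissimilar | Cluster-control |
|---|---|---|---|
| 0, 0 | 5.1 | 5.2 | 5.1 |
| 0, 0.5 | 2.1 | 2.1 | 2.1 |
| 0, 1.0 | 0.6 | 0.6 | 0.7 |
| 0.25, 0 | 7.7 | 5.5 | 4.2 |
| 0.25, 0.5 | 4.7 | 3.2 | 2.0 |
| 0.25, 1.0 | 2.4 | 1.4 | 0.8 |
| 0.5, 0 | 11.4 | 6.5 | 3.0 |
| 0.5, 0.5 | 8.7 | 4.6 | 2.0 |
| 0.5, 1.0 | 6.7 | 3.1 | 1.0 |
| 1.0, 0 | 12.3 | 6.0 | 2.4 |
| 1.0, 0.5 | 11.6 | 5.7 | 2.5 |
| 1.0, 1.0 | 10.8 | 5.3 | 2.0 |

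The first row shows that the test is sound without dependence. Independent pairs with the same skewed distributions gave 4.5-5.8%, so skewness is not the cause. Results for 10 and 20 Centers are similar.

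**Other pairings.**
- Each case's two controls form only one pair (37 control pairs): 0.8-7.0% over the settings run.
- Literal 15.1.1 (dissimilar pairs are patients from different clusters in one Center; 2 / 6 clusters per Center; 10,000 studies): 3.4/3.6% at CVs (0.25, 0), 1.7/1.3% at (0.5, 0), 0.9/0.6% at (0.5, 0.5), 0.7/0.8% at (1.0, 0.5), and down to about 0.3% at Center CV 1.0.

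**Second model.** Normal data, 20 Centers with 3 cases each, Center share vc; control-control / all dissimilar / cluster-control: vp 0.2, vc 0 gives 11.9 / 7.3 / 3.3%; vp 0, vc 0.5 gives 0.8 / 0.8 / 0.9%; vp 0.2, vc 0.3 gives 8.9 / 4.0 / 1.1%. Both directions appear again.

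**Remedies.** Under the first model, six settings and the three control-based comparators: permutation within Center 3.8-5.9% (2,000 studies, SE about 0.5 points); mixed model on log(1 + overlaps) 4.6-6.2% (4,000 studies). With the different-cluster comparator: 4.7-5.1% and 5.3-5.5%.

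**The case against.** The strongest reply is that the protocol does not restrict the dissimilar pairs, so with controls included the natural comparator is all of them. In the central range that gives 4.6-6.5%, no worse than the proposed mixed model. In the first model, inflation beyond 7% arises only when control-control pairs are the sole comparator, and the protocol does not say that controls are all paired with one another or come from the same Center. These facts stand, and they limit what can be said about false positives. They do not show control. The near-nominal figures come from opposing errors that happen to cancel: the same column falls to 0.6% when Centers differ and attendance does not, and under the normal model with 20 Centers of 3 cases it runs from 0.8% to 9.4% (vp 0.4).

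A second reply is that the t-test is called the simplest form, no significance level or decision rule is set, and an SAP may supply methods for correlated data. This limits the seriousness but does not remove the point. The protocol names the test in three places, one of them the primary endpoint section. An SAP that follows it inherits the error, and one that corrects it contradicts the protocol.

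Third, the regressions are affected only conditionally: the linear model if fitted on pairs with ordinary standard errors, the logistic model only if fitted on pairs and not by subject. That is right.

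Finally, the mixed model was checked only with one common window, whereas the study's windows differ by pair. Its use with window length as a covariate is reasonable but untested.

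**Conclusion.** The concern holds. The stated test fails its own independence assumption under the protocol's own pairing rule, and its p-values cannot be taken at face value. No single error rate can be quoted, because the protocol gives neither the variance components nor the comparator. For the 15-Center design, the illustrations at an assumed 5% level run from about 0.3% to 12.3%; inflation is clearest against control-control pairs, and the test is conservative against cluster-control pairs and on the literal reading of 15.1.1. These figures rest on the assumed attendance and Center variation, same-Center controls and a common window. That the error is uncontrolled does not rest on them. The study can proceed, but the analysis should be changed.

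**What to change.** Keep the pair-level descriptive statistics. In 15.1, 15.3 and the synopsis, state which dissimilar pairs form the comparator, and amend 15.1.1 so that it agrees with the use of controls elsewhere. Replace the plain 2-sample t-test, and any plain pair-level regression, with one of these:

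- a mixed model with random effects for both members of the pair and a Center term, with window length as a covariate; this can use the windows as collected, but its error rate should first be checked by simulation with pair-specific windows;
- a permutation of patient labels within Center, if overlap is available for all within-Center pairs over comparable windows.

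If the logistic model is fitted by subject, allow for strain cluster and Center.

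The cost is analysis wording and modest programming. The mixed model needs no new data. The permutation may need further chart abstraction, because date ranges are specific to each pair. P-values may move in either direction.

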15.1.1 Data Sets Analyzed

All analyses will be based on the group of subjects that are identified by the CO-RDP as having NTM isolates, defined as highly similar strains at the genomic level, harbored by two or more patients within a single Care Center.

152 Demographic and Baseline Characteristics

The following baseline demographic and clinical characteristics will be reported: age, gender, race, ethnicity, zip code, and NTM sub/species.

153 Analysis of Primary Endpoint

PART A / Epidemiologic Investigation:

The primary endpoint will characterize the origins and prevalence of healthcare-associated patient-to-patient transmission of NTM among different CF Care Centers. We will further characterize the source(s) of direct or indirect transmission of NTM within an individual CF healthcare setting. We will identify a set of variables used to assess degree of proximity of subjects in time and/or space. For example, two subjects with neighboring rooms at a hospital would have close proximity, but proximity would be increased for two subjects at a facility that had longer overlap time, relative to a pair of subjects that had shorter overlap. We will explore creating composite measures of quantitative proximity that incorporate multiple variables. Qualitative measures of proximity, such as location type (testing laboratory, patient room) will also be assessed. Several testing approaches will be used to compare the relationship between similarity of strains and degree of proximity of subjects. In the simplest form, descriptive statistics will be computed for proximity variables, for pairs of subjects who are determined to have similar strains versus those who have dissimilar strains, and multivariate or 2-sample t-tests will be performed to test for differences between these groups. More advanced modeling will be performed to determine the relationship between the degree of similarity in strains with the proximity and subject characteristic variables; multiple linear regression will be used when considering continuous strain similarity, while multiple logistic regression will be used when considering subjects with dichotomized (similar/dissimilar) strains to other subjects.

PART B / Water Biofilm Collection:

The primary endpoint will characterize clinically-relevant NTM found in water biofilms within CF healthcare settings and determine if the biofilm isolates are highly related to isolates recovered from patients.

154 Analysis of Secondary Endpoints

PART A / Epidemiologic Investigation:

The secondary endpoints will characterize CF Center adherence to the CF IP&C guidelines as well as characterize points of patient overlap. Basic summaries of points of potential transmission overlap will be provided.

PART B / Water Biofilm Collection:

The incidence and prevalence of NTM species and subspecies within healthcare water biofilms will be characterized. Comparisons of NTM biofilm isolates and highly related patient isolates will be provided.

155 Interim Analysis

No formal interim analysis involving a data monitoring committee (DMC) is planned. However, annual reports summarizing key variables related to site enrollment and adherence to protocol

will be generated. These reports will help guide protocol revisions. Details of the planned analysis for these annual reports can be found in the Statistical Analysis Plan (SAP).

